### **Recruitment**

Subjects will be recruited from the outpatient clinics at the Washington DC VAMC. The DC VAMC annually has over 100 admissions for stroke. [name], has WOC status at the DC VAMC and will confirm that patients meet study criteria. Additionally, veterans will be recruited from nearby MedStar National Rehabilitation Hospital (NRH), Washington Hospital Center (WHC), and Medstar Health outpatient clinics.

The inclusion criteria are: 1) Age 21 or older; 2) ischemic or hemorrhagic stroke (with confirmatory neuroimaging) that occurred more than 6 months before entering the study; 3) presence of voluntary hand activity indicated by a score of at least 1 on the finger mass extension/grasp release item of the Fugl-Meyer Test of Motor Function; 4) adequate cognitive status, as determined by Mini-Mental Status Examination (Bleeker 1988) score >24; 5) no upper extremity injury or conditions that limited use prior to the stroke. Subjects will be excluded if they: 1) cannot give informed consent; 2) have clinically significant fluctuations in mental status within a month of enrollment; 3) were not independent prior to the stroke as measured by scores <95 on the Barthel Index (de Morton 2008) or >1 on the Modified Rankin Scale (Quinn 2009); 4) have hemispatial neglect as determined by >3 errors on the Star Cancellation Test (Manly 2009); 5) have severe sensory loss as determined by a score of 2 on the sensory item of the NIHSS (Lai 1988); 6) receiving oral or injected antispasticity medications during study treatment; 7) pain that interferes with daily activities; 8) history of prior stroke.

In a previous study in chronic stroke, we found that the dropout rate was 16.7%, so we will plan to **recruit 46 subjects**. Subjects who drop out of the study will be replaced until a total of **38 subjects complete the protocols**. All therapy will be in addition to the regular PT and OT subjects may be receiving as part of their outpatient treatment. The amount of outside PT or OT targeting arm or hand function received by subjects while enrolled in the study will be logged and used as a potential covariate in the analysis.

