### Data analysis

Prior to conducting the main analyses, summary statistics, histograms, and scatter plots will be inspected to verify that distribution assumptions are met. Adjustments (e.g., transformations) to the main dependent measures will be made as necessary to address any problems (e.g., skewness, outliers) that these preliminary analyses uncover. To test Hypotheses, a series of mixed model ANOVAs will be tested, one for each dependent variable, with the within-subject variable being timepoint (pre, after 12 hours of treatment, after 24 hours of treatment, 6 month followup) and the between-subject variable of group (experimental vs. control). A significant effect of timepoint or a significant timepoint x group interaction would be followed with a series of paired t-tests, with Bonferoni corrections. Hypothesis I will be tested with a paired t-test between the pre and post-robotic timepoint (after 12 hours of robotic treatment). Hypothesis II will be tested with a paired t-test between the pre and post-treatment timepoint in the experimental group (after 12 hours of robot and 12 hours of conventional therapy). Additionally a z-test will be performed for the hypothesis that the proportion of subjects with 10% or greater gain at the post-treatment timepoint is significantly greater than zero. A final paired t-test and z-test between pre and 6-month followup timepoints will be performed. If a change is statistically significant, mean changes will be compared to predetermined MCID values of 10% of full scale. To test Hypothesis III, the timepoint x group interaction effect will be examined in the mixed model ANOVA. If significant, gains in the dependent variables will be calculated at the post-treatment and 6-month timepoints (relative to the pre timepoint), and between-group differences will be tested with unpaired t-tests, with Bonferoni corrections.

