In secondary analysis, we will look to identify the characteristics of patients who are most responsive to the treatment. Potential predictors include initial impairment level, and time-varying predictors such as amount of home use (MAL) at the previous assessment. The subjects will be divided into severe (Fugl-Meyer<30), moderate (30<Fugl-Meyer<50) and mild impairment groups (Fugl-Meyer>50). This division is based on a previous study that reported subjects with initially moderate impairment (Fugl-Meyer = 40) benefited the most from robotic therapy, with reduced effectiveness in severe and mildly impaired subjects (Hsieh 2012). The dependent variables will be gain in the FM, ARAT and MAL at each timepoint. A fixed effects (mixed) model will be used to determine if the gains over time were the same across the 3 impairment groups, and whether use at home in the preceding time interval predicts later improvement.

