To address Hypothesis III, we calculated the power to detect the expected differences in gains between the experimental and control groups. The experimental treatment in our pilot study produced gains of 7 (sd=4.9) in the Fugl-Meyer. A recent study reported gains of 2.47 (sd=1.67) on the Fugl-Meyer after 24 hours of conventional therapy in 35 stroke subjects with similar intake Fugl-Meyer scores as in our pilot study (FM = 22.4 vs. 21) (Klamroth-Marganska 2014). Using these data, the mean difference in treatments will have an effect size of 1.9. For a 1-tailed unpaired t-test, **N=5** subjects in each treatment group are needed to detect this difference with power > 0.80. Similarly for the ARAT, we had gains of 5.6 (sd=4.7) after the experimental treatment in our pilot study. A different study (Fleming 2015) reported gains of 1.0 (sd=5.7) after 24 hours of conventional therapy in 17 chronic stroke subjects with similar intake ARAT scores as in our pilot study (ARAT = 26.6 vs. 20.9). Using these data, the mean difference in treatments will have an effect size of 0.84. For a 1-tailed unpaired t-test, **N=19** subjects in each treatment group will detect this difference with power > 0.80.

Therefore with **N=19** subjects in each treatment group, we will detect the anticipated pre-post changes and group differences in the ARAT and Fugl-Meyer. We had a dropout rate of 0.167 in the pilot study. Therefore, we will plan for this and recruit 23 subjects into each treatment group. We have no pilot data on the MAL to perform a power analysis for the outcome.

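### The home-use analysis does not say what 'gain' is measured from; if it is measured from pre-treatment, two of three gains partly precede the MAL predictor and cannot show later improvement

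*Combined protocol and SAP*

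**What the plan says.** The second part of the Data analysis subsection (section 5, Study Design) describes a secondary analysis of who responds to treatment. One candidate predictor is "time-varying predictors such as amount of home use (MAL) at the previous assessment". On outcomes it says: "The dependent variables will be gain in the FM, ARAT and MAL at each timepoint". The model has two purposes. The first concerns impairment: "A fixed effects (mixed) model will be used to determine if the gains over time were the same across the 3 impairment groups". The second is to learn "whether use at home in the preceding time interval predicts later improvement".

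This text gives no reference visit for gain. The only definition in the subsection belongs to the follow-up tests for Hypothesis III: "gains in the dependent variables will be calculated at the post-treatment and 6-month timepoints (relative to the pre timepoint". Visits are defined for the main model as "timepoint (pre, after 12 hours of treatment, after 24 hours of treatment, 6 month followup", which gives three gains per subject. Nothing in the secondary analysis mentions change between successive visits or adjustment for the outcome at the previous visit.

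**The concern.** The question is about time order: does use of the arm at one visit predict what happens afterwards? If gain is counted from pre-treatment, the 24-hour gain contains the change made by 12 hours, which is when the lagged MAL is recorded. The 6-month gain likewise contains everything gained by 24 hours. Someone who improved early would both use the arm more at home and carry that early gain into later totals. The model could then return a positive coefficient although home use had no bearing on later change. This applies to FM and ARAT as well as to MAL.

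At stake is how a positive home-use result would be read. It could be reported as evidence that use precedes recovery when it shows only that early improvers kept their gains.

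**Working it through.** **1. Size of the analysis.** The documents give no figure for this model, so its size comes from the Power Analysis. For ARAT, "the mean difference in treatments will have an effect size of 0.84". The mean difference is 5.6 − 1.0 = 4.6. Taking 6 robot-first pilot subjects (assumed, half of 12) and 17 comparison subjects, the pooled SD is √[(5 × 4.7² + 16 × 5.7²)/21] = √30.01 = 5.48, and 4.6/5.48 = 0.84. One-tailed t-test power is 0.795 with 18 per group and 0.815 with 19, so 19 per group reproduces. That gives 38 completers, matching the Recruitment text, "until a total of 38 subjects complete the protocols". Allowing for dropout, 38/(1 − 0.167) = 45.6, or 46.

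**2. Where the overlap lies.** Let d1, d2, d3 be the MAL changes and f1, f2, f3 the FM changes in the three intervals. Prior use has no effect on the next change, and errors are independent. Let r be the correlation of MAL and FM changes within an interval.

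| Gain from pre | Lagged MAL | Covariance with FM gain |
|---|---|---|
| 12 h: f1 | pre | 0 |
| 24 h: f1 + f2 | pre + d1 | cov(d1, f1) |
| 6 months: f1 + f2 + f3 | pre + d1 + d2 | cov(d1, f1) + cov(d2, f2) |

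The FM change SD per interval is about 4.9/√2 = 3.5, from the pilot 24-hour SD of 4.9. With an assumed MAL change SD of 0.5, the last two covariances are 0.5 × 3.5 × r = 1.75r and 3.5r. With visit-to-visit change as the outcome, all three are zero. Two of three gains are affected, and only if r is not zero.

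**3. False findings, FM outcome.** Simulation of 38 subjects with three gains each, 500 runs per setting, true effect zero. The model had lagged MAL, visit, thirds of baseline FM and a random intercept; arm was not included. Tests were two-sided at 5% (assumed), so 2.5% is expected in each direction. Further inputs assumed because the documents give none: baseline MAL SD 1.1, baseline FM SD 12, FM error SD 1.5, baseline MAL-FM correlation 0.5. Monte Carlo standard error is at most √(0.25/500) = 2.2 points.

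| r | Gain from pre, random intercept | Gain from pre, subject fixed effects | Visit-to-visit change | Next FM adjusted for previous FM |
|---|---|---|---|---|
| 0 | 4.2% | 3.4% | 2.4% | 3.6% |
| 0.2 | 10.0% | 5.6% | 2.0% | 4.4% |
| 0.3 | 14.8% | 5.2% | 2.4% | 4.4% |
| 0.5 | 23.8% | 13.0% | 1.8% | 4.4% |
| 0.7 | 45.8% | 19.0% | 1.2% | 3.6% |

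Entries are positive-direction rejections. A repeat simulation of the random-intercept model gave 4%, 15%, 25% and 37% at r = 0, 0.3, 0.5 and 0.7. With MAL change SD 0.25 the random-intercept rates at r = 0.3 and 0.5 are 9.0% and 15.2%; with SD 0.8 they are 18.6% and 36.8%. If people also differ in overall responsiveness, they are 37% and 70% (32% and 62% with subject fixed effects). In that setting the two alternatives give 4.0-6.2% and 3.4-6.4%. ARAT was not simulated; the algebra in step 2 is the same.

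**4. MAL as its own outcome.** With MAL error variance σe² and change variance σd², the covariances of lagged MAL with gain from pre are −σe², +σd² and +2σd². With visit-to-visit change each is −σe², which is regression to the mean. The fitted sign also depends on how the mixed model weights within-subject information, so it was simulated.

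| Error SD | Change SD | Gain from pre: false + / false − | Visit-to-visit: false − |
|---|---|---|---|
| 0 | 0.25 | 47.6% / 0% | 2.6% |
| 0 | 0.5 | 86.2% / 0% | 4.2% |
| 0 | 0.8 | 94.6% / 0% | 12.6% |
| 0.3 | 0.25 | 1.4% / 4.0% | 48.4% |
| 0.3 | 0.5 | 35.0% / 0.6% | 27.6% |
| 0.3 | 0.8 | 75.0% / 0% | 26.0% |
| 0.5 | 0.25 | 0% / 28.8% | 95.6% |
| 0.5 | 0.5 | 4.2% / 2.4% | 83.6% |
| 0.5 | 0.8 | 42.8% / 0% | 56.6% |

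**The case against.** The strongest reply is that the plan never says this gain is measured from pre-treatment. The definition quoted above serves the Hypothesis III tests, applies only after a significant interaction, and covers two visits rather than all of them. The secondary text speaks of a preceding interval and of later improvement, which could mean change between visits. This stands in part: the cumulative reading is an inference, although it follows the only definition given. The other reading clears FM and ARAT but leaves MAL on lagged MAL biased by regression to the mean, so the text needs an edit either way.

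Second, a reader might infer that the analysis is bound to find that home use predicts improvement. The documents do not support that. The first gain has no overlap, the FM rate is near nominal when MAL and FM changes are unrelated, and subject fixed effects, another possible reading of the model description, give lower rates. For MAL the bias can be negative. The MAL variances, error and correlations are all assumed; the Power Analysis says there are no pilot data on the MAL.

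Third, the predictors are only potential ones in a secondary analysis. That is correct and limits the weight of the point. It does not make a positive coefficient interpretable.

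**Conclusion.** The point holds as a defect of definition with a consequence for interpretation. As written, the reference visit is missing. On the best-supported reading, two of three gains per subject include change that came before the predictor, so a positive coefficient cannot support a statement about later improvement. For FM with a random intercept, the false positive-direction rate is close to the nominal 2.5% with unrelated changes and about 15-45% at assumed correlations of 0.3-0.7. For MAL as its own outcome, bias arises under either meaning of gain; its direction and size depend on measurement error that the documents do not give.

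A reader might extend this to the whole responder analysis or to the trial's main conclusions. Neither follows. Comparing gains across impairment groups does not depend on lagged MAL, and Hypotheses I-III and the sample size are unaffected. This is a cheap improvement to an exploratory analysis.

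**What to change.** In the secondary-analysis text, define later improvement as the change in FM and ARAT from the visit at which MAL was measured to the next visit: pre to 12 hours, 12 to 24 hours, 24 hours to 6 months. Modelling the next score adjusted for the score at the MAL visit is an acceptable alternative. Include lagged MAL, interval and arm, and state the random-effects structure, since the rates depend on it. Do not use MAL gain as an outcome when lagged MAL is the predictor, or give it a separate analysis that deals with regression to the mean.

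The cost is a few sentences; visits and data stay the same. Interval changes are somewhat noisier than cumulative gains. If people differ in overall responsiveness, the false positive-direction rate stays slightly above nominal (about 3-6% in the simulations), so a positive result should still be reported as exploratory.

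### The secondary analysis asks who responds best to the treatment, but as written it compares gains by impairment group with no arm-by-impairment term; as a minor point, Fugl-Meyer scores of 30 and 50 fall in no group

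*Combined protocol and SAP*

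**What the plan says.** All of this is in section 5, Study Design.

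- **Aim.** The last paragraph under Data analysis says "we will look to identify the characteristics of patients who are most responsive to the treatment".
- **Strata.** "The subjects will be divided into severe (Fugl-Meyer<30), moderate (30<Fugl-Meyer<50) and mild impairment groups (Fugl-Meyer>50". The cut-points come from a published study in which moderately impaired subjects "benefited the most from robotic therapy, with reduced effectiveness in severe and mildly impaired subjects".
- **Outcomes.** "The dependent variables will be gain in the FM, ARAT and MAL at each timepoint".
- **Model.** A mixed model is to be used "to determine if the gains over time were the same across the 3 impairment groups", and to see whether home use in the preceding interval predicts later improvement.
- **Treatment arm.** The main model, in the paragraph before, includes "the between-subject variable of group (experimental vs. control") and a timepoint × group interaction, but no impairment term. The secondary paragraph names no arm and does not say whether the two arms are pooled or only the experimental arm is used.

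**The concern.** Asking who responds best to a treatment, with strata justified by differential benefit from robotic therapy, is a question of effect modification: does the difference between arms vary with baseline impairment? The stated test asks something else, namely whether raw gain varies with baseline impairment.

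Raw gain can differ between strata for reasons that operate in both arms. One is general prognosis. For FM gain there are two more. Baseline FM both defines the stratum and is subtracted in the outcome. The protocol itself (Clinical evaluations) also describes the FM as less responsive in mildly impaired subjects. A stratum difference from the written model could therefore be read as indicating who should receive the robot treatment when it reflects none of that.

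A smaller point is that the stratum definitions use strict inequalities on both sides of each cut, so two attainable scores belong to no group.

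**Working it through.** **1. The plan's own figure.** The secondary analysis has no sample-size figure, so the base is the Hypothesis III calculation for the ARAT (Power Analysis): effect size 0.84, one-tailed unpaired t-test, 19 per group, power above 0.80. With α = 0.05 (stated for the paired tests, assumed here), the noncentral t gives power 0.815 at n = 19 per group. Dropout: 19/(1 − 0.167) = 22.8, rounded up to 23 per group. Both figures reproduce. Completers: 2 × 19 = 38.

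**2. What the written comparison estimates.** Let mean gain in stratum s be μ_s in the control arm and μ_s + τ_s in the experimental arm. The question is whether the τ_s differ.

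- Arms pooled with equal allocation: stratum mean = μ_s + τ_s/2.
- Experimental arm only: stratum mean = μ_s + τ_s.

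Neither isolates τ_s. Arm as a main effect alone does not help either, because the stratum effect still carries μ_s. Only arm × stratum estimates differences in τ_s. Restricting to the experimental arm has a further difficulty: half of its 24 hours are the same conventional therapy that the control arm receives.

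**3. Illustration by simulation.** Assumptions: 6 subjects per arm-by-stratum cell, SD 1, one timepoint, 4,000 runs, two-degree-of-freedom F tests at 0.05.

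| Scenario (severe, moderate, mild) | μ_s | τ_s | Pooled stratum test rejects | Interaction test rejects |
|---|---|---|---|---|
| A. Prognosis only | 0, 1, 0 | 0.84, 0.84, 0.84 | 60.3% | 4.6% |
| B. Differential benefit, equal pooled means | 0.84, −0.42, 0.84 | −0.84, 1.68, −0.84 | 2.0% | 86.5% |
| C. Benefit in moderate only, flat prognosis | 0, 0, 0 | 0, 0.84, 0 | 14.4% | 16.1% |

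In A the written comparison signals a difference though no stratum benefits more. In B it misses a large one. In C both tests are weak.

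**4. Baseline dependence of FM gain.** The slope of gain on baseline is r × (SD_post/SD_pre) − 1. The Power Analysis gives FM pre-post correlations of 0.85 and 0.91. Assuming equal pre and post SDs, the slopes are −0.15 and −0.09 points per baseline point. For strata whose means are 30 points apart (assumption), expected gains differ by 30 × 0.09 = 2.7 to 30 × 0.15 = 4.5 points. If the same r holds in both arms, this appears with no differential treatment effect. For comparison, the whole expected FM difference between arms is 7 − 2.47 = 4.53. The direct subtraction applies to FM gain only, not to ARAT or MAL.

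**5. Unassigned scores.** Ten percent of full scale is 6.6 points, so full scale is 66. Items are scored on three points, so totals are whole numbers from 0 to 66, which is 67 values. Two of them, 30 and 50, satisfy none of the three definitions. With an even spread, 46 × 2/67 = 1.4 subjects. Across the assumed baseline distributions tried (even, or normal with mean 21–40 and SD 8–12), 1.2–2.2 of 46 subjects are unassigned, with a 71–89% chance of at least one.

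**6. What an interaction could deliver.** Take 38 completers in equal strata (assumption), so 38/6 = 6.33 per cell, residual df 32, benefit 0.84 SD in the moderate stratum and 0 elsewhere, two-sided 0.05.

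- Moderate vs severe: SE = √(2/6.33 + 2/6.33) = 0.795; 0.84/0.795 = 1.06; power 0.18.
- Moderate vs the mean of the others: SE = √(1.5 × 2/6.33) = 0.688; 0.84/0.688 = 1.22; power 0.22.
- Two-df test: noncentrality (6.33/2) × (0.28² + 0.56² + 0.28²) = 1.49; power 0.17.
- Moderate-vs-severe difference needed for 80% power: 0.795 × (2.037 + 0.842) = 2.3 SD.

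Uneven strata (10, 6, 3 or 12, 5, 2 per arm) give powers of 0.16–0.20 and a required difference of 2.1–2.2 SD.

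**The case against.** The best defence is that the paragraph is short and lists no model terms in full. The preceding paragraph has arm in every main model, so an arm interaction may be intended. The text can also be read as a search for predictors of gain, since it speaks of potential predictors and asks whether home use predicts later improvement. That is a legitimate secondary aim. Part of this stands: the plan does not rule the interaction out. But the comparison it does state targets a different quantity from its stated aim, and its rationale for the strata is differential benefit from robotic therapy. If only prognosis is meant, the text should say so.

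Several stronger readings are tempting but not supported:

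- A reader might infer that the boundary gap helps defeat the analysis, or that subjects scoring 30 or 50 are excluded. The gap is minor and separate, and nothing in the documents says they are dropped.
- A reader might note that a baseline FM of 60 or more cannot rise by 6.6 points. That concerns the 10%-gain z-test in the main analysis. This analysis uses gain itself, and the pilot intake FM was about 21.
- A reader might extend the baseline-subtraction argument to all three outcomes. It applies directly to FM gain only.
- A reader might cite about 6 subjects per cell as a fault of the plan. That figure assumes equal strata and arises only once arm is crossed with severity. The three groups as written would average 38/3 = 12.7.
- A reader might hold that a continuous score with a quadratic term is essential. Three ordered categories can show a mid-range peak, so this is a preference.

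The simulation shows the risk under assumed effects and pooling. It does not show what this trial's data will do.

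**Conclusion.** The point holds as a recommended change to a secondary analysis. Followed as written, with arms pooled or with the experimental arm alone, the comparison cannot separate general prognosis from benefit specific to the robot plus conventional treatment. For FM gain, baseline dependence and lower responsiveness in mild subjects add to the confusion.

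The size of the problem depends on how strongly impairment predicts gain in both arms, which the documents do not give. The 60% versus 4.6% contrast rests on an assumed 1 SD prognostic difference and 6 subjects per cell. The unassigned scores are a small definitional error affecting roughly 1 to 2 of 46 subjects under assumed distributions.

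A reader might infer that the trial's main conclusions are at risk. They are not: no hypothesis and no power statement rests on this analysis. Nor do the documents say that its results will be issued as guidance on selecting patients.

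**What to change.** For gains in FM, ARAT and MAL, state that the repeated-measures mixed model includes arm, baseline FM and arm × baseline FM, allowing the interaction to vary by timepoint if wanted. Keep baseline FM continuous by preference; a quadratic term and its interaction with arm are optional, to allow a mid-range peak. Keep the lagged home-use predictor. Because home use after baseline may itself be affected by arm, report the interaction with and without it.

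Base any statement about who responds to the treatment on the interaction estimate with its confidence interval, labelled exploratory. Describe stratum differences in raw gain as prognostic. Make any displayed categories exhaustive, for example <30, 30–50, >50.

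The cost is a few sentences of SAP text and no new data. The drawback is imprecision: with 38 completers and roughly equal strata, power is about 16–22% for a 0.84 SD benefit confined to one stratum, so the result can only generate hypotheses. The continuous and quadratic versions were not evaluated for power.

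### The three-band comparison of gains by initial Fugl-Meyer is unlikely to have a usable mild band; a continuous, curved baseline Fugl-Meyer term would serve the question better

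*Combined protocol and SAP*

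**What the plan says.** Section 5, Data analysis, sets out a secondary analysis of who responds best. Initial impairment is one candidate predictor, and it enters as three fixed bands: "The subjects will be divided into severe (Fugl-Meyer<30), moderate (30<Fugl-Meyer<50) and mild impairment groups (Fugl-Meyer>50". The outcomes cover all three main measures: "The dependent variables will be gain in the FM, ARAT and MAL at each timepoint". A mixed model is then used "to determine if the gains over time were the same across the 3 impairment groups". The reason given for the cut points is a published finding that "subjects with initially moderate impairment (Fugl-Meyer = 40) benefited the most from robotic therapy, with reduced effectiveness in severe and mildly impaired subjects".

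The Power Analysis describes the outside study that supplied the conventional-therapy Fugl-Meyer gains as having "similar intake Fugl-Meyer scores as in our pilot study (FM = 22.4 vs. 21". Both means fall in the severe band. Completers are fixed under Recruitment: "Subjects who drop out of the study will be replaced until a total of 38 subjects complete the protocols".

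The eligibility criteria set no floor or ceiling on the total Fugl-Meyer score; they require only a minimum on one hand item. The documents give no expected band sizes, no enrolment stratified by Fugl-Meyer, and no rule for a sparse or empty band.

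**The concern.** A three-group comparison needs subjects in all three groups. With an intake mean near 21 or 22, a score above 50 is a rare event in a sample of 38, and nothing in the recruitment plan ensures that such subjects enrol.

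The published pattern behind the cut points is a rise and then a fall, with moderate subjects gaining most. The fall can be seen only if there are subjects on the upper side. If the mild band turns out to hold nobody, or one or two people across both arms, the planned three-level factor cannot be fitted as written or has one level that is barely informed. The bands would then be regrouped after the data are seen. The natural regrouping, below 30 against the rest, is a coarse summary of a score that is measured in full.

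**Working it through.** **1. The plan's own sample size, as a check on the inputs.** For a 1-tailed unpaired t-test with effect size 0.84 and alpha 0.05, the exact noncentral-t calculation gives 19 per group (power 0.815). Allowing for dropout, 19/(1 - 0.167) = 22.8, so 23 per group. Both agree with the Power Analysis. The plan states no band sizes, so there is no further figure to reproduce.

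**2. Baseline SD (an assumption, not a stated figure).** Two inputs come from the Power Analysis, both for robot therapy followed by conventional therapy: "The experimental treatment in our pilot study produced gains of 7 (sd=4.9) in the Fugl-Meyer", and a pre-post correlation of 0.91. If the pre and post SDs are equal, the SD of the gain is SD × sqrt(2(1 - r)). Hence

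SD = 4.9 / sqrt(2 × 0.09) = 4.9 / 0.424 = 11.5.

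The Background gives this gain as 7 ± 2.2. If 2.2 is a standard error, n is about (4.9/2.2)² = 5, so the 11.5 is soft and must be varied.

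**3. Expected band counts at SD 11.5.** Assuming approximate normality, severe = 38 × Φ((30 - mean)/SD) and mild = 38 × [1 - Φ((50 - mean)/SD)].

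| Intake mean | z at 30 | z at 50 | Severe | Moderate | Mild | Chance of no mild subject |
|---|---|---|---|---|---|---|
| 21 | 0.78 | 2.51 | 29.7 | 8.0 | 0.23 | 0.795 |
| 22.4 | 0.66 | 2.39 | 28.3 | 9.4 | 0.32 | 0.725 |

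**4. Sensitivity to the SD (means 21 and 22.4, N = 38).**

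| SD | Severe | Mild |
|---|---|---|
| 8 | 33.1, 31.5 | 0.01, 0.01 |
| 10 | 31.0, 29.5 | 0.07, 0.11 |
| 13 | 28.7, 27.4 | 0.49, 0.64 |
| 15 | 27.6, 26.4 | 1.01, 1.25 |
| 18 | 26.3, 25.2 | 2.04, 2.38 |
| 20 | 25.6, 24.6 | 2.79, 3.18 |

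At SD 11.5, truncating the distribution to the 0-66 scale gives severe 29.4 and 28.0, mild 0.24 and 0.33. Counting all 46 recruits gives severe 36.0 and 34.3, mild 0.28 and 0.39.

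**5. Sensitivity to the mean (SD 11.5).** These means are illustrative; the documents do not give them. A mean of 30 gives 1.6 mild, 35 gives 3.7 (with severe down to 12.6), and 40 gives 7.3. An expected six mild subjects needs a mean near 38, or an SD near 28-29 at the plan's means.

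**6. What the remaining split costs.** With no usable mild band, what is left is roughly 75% severe against 25% not severe. The efficiency of such a split relative to the continuous score, for a linear trend in a normal predictor, is φ(z)²/(p(1 - p)). At p = 0.25, z = 0.674 and φ(z) = 0.318, so 0.318²/0.1875 = 0.54. At the exact proportions above 30 (0.218 and 0.255) it is 0.51 and 0.54. Nearly half the information on a linear trend is lost. This figure applies to a linear trend only; it does not measure the loss for a mid-range peak.

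**The case against.** The inputs are thin. The SD is back-calculated from about five people under an equal-variance assumption. The mean of 21 comes from a small pilot, and 22.4 from an outside study. The binding sample size of 19 per group comes from the ARAT comparison, not the Fugl-Meyer. The documents do not say whether the pilot used the present eligibility criteria, which require some voluntary hand movement. All of this stands, and it is why the counts are given as ranges. It does not rescue the mild band: within SDs of 8 to 20, its expected size at the plan's means never exceeds about 3 of 38, over two arms. A markedly less impaired intake would change the picture, and the documents give no sign of one.

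A reader might infer that the three-group analysis cannot be done at all. The figures do not support that. With 28-30 severe and 8-9 moderate subjects, the moderate-versus-severe contrast remains estimable; it is the mild contrast that is at risk. Nor is an empty mild band certain: at SD 11.5 the chance is about 0.73 to 0.80, and it falls as the SD rises. A reader might also infer that collapsing the bands throws away most of the information. At about 54% retained for a linear trend, it does not.

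Two objections to a continuous model also stand. A straight line cannot show a mid-range peak, so curvature has to be in the model. And if nobody scores above 50, no model can say anything there; the fitted curve would only extrapolate.

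Finally, this is a secondary, exploratory analysis with a published reason for its cut points, and an empty band would be plain at the first baseline table. That limits the weight of the point but does not make the bands the better method.

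**Conclusion.** The point holds as a modest improvement to a secondary analysis. On the plan's intake means, with approximate normality and a derived SD of about 11.5, 38 completers are expected to include 28-30 severe, 8-9 moderate and fewer than one mild subject. Allowing SDs of 8 to 20 gives about 25-33 severe and 0.01-3.2 mild. A mean of 35 at SD 11.5 would give about 3.7 mild. The mild contrast is therefore not expected to be estimable with useful precision, and the severe/non-severe split that remains keeps about 54% of the information on a linear trend.

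This is a projection from the planned intake, not a finding about the enrolled sample. It would be inaccurate to extend it to the main comparisons: none of Hypotheses I-III uses the bands.

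**What to change.** In Section 5, Data analysis, replace the three bands in the gain model with baseline Fugl-Meyer as a continuous predictor. Prespecify linear and quadratic terms, or a spline, as part of the model and not as an optional check, because the rationale is a peak at moderate impairment. Keep the bands for descriptive tables only. State that conclusions will be limited to the observed range of baseline scores, and report that range.

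The cost is wording: baseline Fugl-Meyer is already collected, and no visit, measurement or sample size changes. The score also uses every subject, including anyone at exactly 30 or 50, whom the printed inequalities place in no band. The drawbacks are that the result is a fitted curve, less familiar to clinical readers than three labelled groups, and that it still says nothing about scores above 50 if no such subjects enrol.
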